4.6 Concomitant Medications/Treatments

The investigator must be informed as soon as possible about any medication taken from the time of screening until the end of the clinical phase of the study (final study visit). Any concomitant medication(s), taken during the study will be recorded.

Investigators may prescribe concomitant medications or treatments (eg, acetaminophen, diphenhydramine) deemed necessary to provide adequate prophylactic or supportive care except for those medications identified as “excluded” as listed in the bulleted list below. Patients may continue baseline medications that were initially deemed appropriate by the investigator at screening.

Subjects must be instructed not to take any medications, including over-the-counter products, without first consulting with the investigator.

The following medications are considered exclusionary during the study:

- Any investigational anticancer therapy (within 28 days prior to registration)
- Any concurrent chemotherapy, radiotherapy (except palliative radiotherapy on non-target lesions only), immunotherapy, biologic or hormonal therapy for cancer treatment. (within 14 days prior to registration, 28 days for systemic chemotherapy)
- Immunosuppressive medications including, but not limited to systemic corticosteroids at doses not exceeding 10 mg/day of prednisone or equivalent, methotrexate, azathioprine, and TNF-alpha blockers. Use of immunosuppressive medications for the management of investigational product-related AEs or in subjects with contrast allergies is acceptable. In addition, use of inhaled and intranasal corticosteroids is permitted. Temporary courses of corticosteroids for treatment of underlying or concurrent illness or in the setting of palliative radiotherapy may be permitted upon discussion with the PI.
- Live attenuated vaccines during the study within 28 days prior to registration through 180 days after the last dose of both drugs
- Herbal and natural remedies (within 14 days prior to registration)

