3.2 Exclusion Criteria

3.2.1 Patients who have had radiotherapy ≤ 14 days prior to registration are not eligible.

3.2.2 Patients who have received systemic chemotherapy or investigational agents ≤ 28 days prior to registration are not eligible.

3.2.3 Patients are not eligible who have had major surgery ≤ 14 days prior to registration. Please contact PI and QAM for questions about specific surgical procedures.

3.2.4 Patients are not eligible who have received prior PARP inhibitors (including but not limited to veliparib, talazoparib, rucaparib, and olaparib).

3.2.5 Patients are not eligible who have received prior immunotherapy including interleukin-2 and immune checkpoint antagonists and/or agonists (including but not limited to PD-1, PD-L1, CD137, or OX40).

NOTE: Single agent anti-CTLA4 monoclonal antibody treatments are permitted. Cancer vaccine therapies are permitted.

3.2.6 Patients with the following histologies are not eligible for either study cohort given known response to PD-1/PD-L1 inhibitor monotherapy:
Non-small cell lung cancer, squamous cell carcinoma of head and neck, melanoma, renal cell carcinoma, bladder cancer, Hodgkin's lymphoma, Merkel cell carcinoma, and MSI-H colorectal cancer

3.2.7 Patients with deleterious BRCA 1/2 mutated ovarian cancer are not eligible.

3.2.8 Patients are not eligible who have had a prior allogeneic stem cell transplant.
NOTE: Autologous stem cell transplant is acceptable.

3.2.9 Patients who are taking any herbal (alternative) medicines are NOT eligible for participation. Patients must be off any such medications by the time of registration for ≥ 14 days.
NOTE: Vitamin supplements are acceptable.

3.2.10 Patients requiring systemic treatment with corticosteroids (>10 mg daily prednisone equivalents) or other immunosuppressive medications ≤ 14 days prior to first dose of study drug are not eligible.
NOTE: Inhaled and intranasal corticosteroids are permitted. A brief (less than 3 weeks) course of corticosteroids for prophylaxis (eg, contrast dye allergy) or for treatment of non-autoimmune conditions (eg, delayed-type

hypersensitivity reaction caused by a contact allergen) is permitted.

- 3.2.11 Patients who receive a live attenuated vaccine ≤ 28 days prior to registration are not eligible.
- 3.2.12 Patients must have no history of CNS metastasis at the screening assessment.

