4.2.1 Veliparib

Veliparib is administered orally twice a day starting on Day 1 of each cycle. Subjects will self-administer the morning and evening doses of veliparib approximately 12 hours apart in the same calendar day. Each dose of veliparib will be taken with a glass of water and consumed over as short a time as possible (i.e., not slower than 1 capsule every 2 minutes) with or without food. During veliparib treatment, standard antiemetic therapy may be administered as appropriate, including a combination of standard antiemetic's (i.e., 5-HT3 receptor antagonists, steroids, and prochlorperazine, and/or promethazine).

It is recommended that if a subject misses a scheduled dose of veliparib and less than 6 hours have passed since the scheduled dosing time, the dose should be immediately taken. It is recommended that if more than 6 hours have passed since the scheduled dosing time, the subject should not take the missed dose but should wait and take the next regularly scheduled dose.

If the subject vomits within 15 minutes of taking veliparib, another dose will be administered. The dose may only be repeated once. If more than 15 minutes has passed from the time of oral dosing then no additional doses will be taken.

Patients will maintain a drug diary for dosing compliance each cycle. Completed drug diaries will be returned at the beginning of each cycle along with any leftover veliparib tablets and drug bottles.

See section 4.3 for details on dose escalation during Phase I and section 4.4 for toxicity management

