10.2 Sample Size and Accrual

The initial study has recruited 3 patients at the lower dose and 6 at the MTD. Of these 6 at the MTD, 4 have genetic mutation of interest, and 2 do not. The study will, due to lack of funding and other reasons recruit 6 more patients with genetic mutation of interest. The response rate will be computed separately for 4+6 = 10 patients with genetic mutation.

Dose Escalation Phase

The expected number of patients in the dose escalation phase will be in the range of 6 to

18 based on the 3+3 design.

Expansion Cohort

The initial study design was to accrue a total of up to 50 patients (for 48 evaluable) to the study in two phases: dose escalation and dose expansion. The original design anticipated a total of 6-18 patients with advanced solid tumors or lymphoma in the dose escalation phase; 9 patients were enrolled, including 6 that were treated at the MTD of 400 mg BID. Due to funding issues, the study will perform an early analysis of preliminary efficacy after the next 6 patients are enrolled in the expansion cohort.

As stated above, in **the modified plan for expansion cohort**, will accrue 6 new patients with genetic alteration for early preliminary efficacy assessment, which together with 4 previously treated patients with genetic mutation will provide total of 6+4=10 patients, with genetic mutation. ORR will be computed at the first imaging (8 weeks). Preliminary efficacy will be evaluated by RECISTv 1.1. As exploratory analysis, irRECIST will be used to obtain preliminary efficacy as well. All ORR will use the first imaging time point whether RECIST or irRECIST.

The study will be considered a success if the lower 90% exact confidence bound will be > 10% , i.e. if three or more successes out of n=10 are observed.

I According to the modified plan for the current trial, the study will be closed after the 6 additional patients will have been recruited.”

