11.6.2 Other Protocol Deviations

All other deviations from the protocol must be reported to the assigned QAM using the appropriate form.

A protocol deviation is any unplanned variance from an IRB approved protocol that:

- Is generally noted or recognized after it occurs.
- Has no substantive effect on the risks to research participants.
- Has no substantive effect on the scientific integrity of the research plan or the value of the data collected.
- Did not result from willful or knowing misconduct on the part of the investigator(s).

A protocol deviation may be considered an instance of Reportable New Information(RNI) if it:

- Has harmed or increased the risk of harm to one or more research participants.
- Has damaged the scientific integrity of the data collected for the study.
- Results from willful or knowing misconduct on the part of the investigator(s).

- Demonstrates serious or continuing noncompliance with federal regulations, State laws, or University policies.

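### Section 4.6 states the 10 mg/day systemic-steroid limit the wrong way round relative to exclusion criterion 3.2.10

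*Combined protocol and SAP*

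**What the plan says.** Three statements in the combined protocol and SAP bear on systemic steroids at or below 10 mg/day of prednisone equivalent.

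- **Entry (Section 3.2, criterion 3.2.10).** The criterion makes ineligible "Patients requiring systemic treatment with corticosteroids (>10 mg daily prednisone equivalents) or other immunosuppressive medications" in the 14 days before the first dose of study drug. Its note permits inhaled and intranasal steroids and brief courses of under three weeks for certain purposes.
- **On study, the list (Section 4.6).** The list opens with "The following medications are considered exclusionary during the study". One bullet covers "Immunosuppressive medications including, but not limited to systemic corticosteroids" and sets the steroid threshold as "systemic corticosteroids at doses not exceeding 10 mg/day of prednisone or equivalent". The bullet then makes exceptions for managing product-related adverse events, contrast allergy, inhaled or intranasal use, and temporary courses discussed with the PI.
- **On study, baseline medications (Section 4.6, before the list).** "Patients may continue baseline medications that were initially deemed appropriate by the investigator at screening".

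Separately, Section 4.2.1 allows steroids within antiemetic combinations ("5-HT3 receptor antagonists, steroids, and prochlorperazine, and/or promethazine").

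**The concern.** The entry rule and the on-study rule use the same 10 mg/day figure with opposite directions. A patient on 5 mg/day of prednisone, for example, passes 3.2.10 but is taking a drug that 4.6 names as barred from the first day of treatment. The baseline-medication sentence points the other way, and nothing expressly says which of the two governs.

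What is at stake is conduct, not inference. Staff must decide whether such a patient stops a maintenance steroid. If the patient continues, they must decide whether that is a deviation, since Section 11.6.2 states that "All other deviations from the protocol must be reported to the assigned QAM using the appropriate form". Two people could apply the section differently and both cite it. Concomitant steroid use is worth handling consistently in a trial of a PD-1 inhibitor.

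**Working it through.** No figure in the plan depends on this wording, so the check compares the texts and bounds the number of patients.

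**1. The two thresholds.** Let *d* be the systemic dose in mg/day of prednisone equivalent.

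| Dose | 3.2.10, at entry | 4.6 as written, on study | 4.6 with *not* deleted |
|---|---|---|---|
| *d* ≤ 10 | not excluded | named as barred | not named |
| *d* > 10 | excluded | not named, but caught by the open-ended class ban | named as barred |

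The range named in 4.6 is the exact complement of the range excluded by 3.2.10.

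**2. Could 4.6 be a deliberately stricter on-study rule?** The two sections cover different periods, so a stricter rule is possible in principle. There are two ways to read it like that, and neither works.

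- If every systemic dose were meant to be barred, the 10 mg/day figure would have no function.
- If only low doses were meant, the rule would single out the less immunosuppressive doses in a bullet about immunosuppression.

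As background on intent only, the Amendment 2 entry in Appendix E gives consistency with 4.6 as the reason for adding steroids to the exclusion criteria. The two sections were meant to agree.

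**3. Do the exceptions resolve it?** The exceptions in 4.6 cover adverse-event management, contrast allergy, inhaled or intranasal use, and temporary courses. Section 4.2.1 covers antiemetic use. None of them covers chronic low-dose systemic maintenance, which is the group that 3.2.10 admits.

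**4. How many patients?** Section 10.2 gives enrolment so far: "The initial study has recruited 3 patients at the lower dose and 6 at the MTD". It plans 6 more.

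- Enrolled: 3 + 6 = 9.
- Total: 9 + 6 = 15.
- Patients on chronic systemic steroids at *d* ≤ 10 outside the exceptions: between 0 and 15 overall, and between 0 and 6 among those still to be enrolled.

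The documents do not narrow this range.

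**The case against.** The strongest reply is that the section can be read so that no problem arises. In 4.6, the carve-out for excluded drugs is attached to what investigators may newly prescribe. The next sentence, on continuing baseline medications, carries no such carve-out. Since 3.2.10 has already screened out higher doses and other immunosuppressives, a low-dose steroid is a natural case for that permission. This is a coherent reading and probably the intended one. It does not settle the matter, because the list heading is unconditional and the permission does not say that it overrides the list.

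A second reply is that the rule is not fully reversed, since doses above 10 mg/day remain barred. That is correct. The error over-restricts low doses and does not open the door to high ones.

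A third is that deleting one word may not be enough, because an open-ended ban could still be said to catch doses that are not named. This has less force after the change. When the named dose is the low one, higher doses are caught all the more; when only doses above 10 mg/day are named, lower doses fall naturally outside. Two mismatches would remain. Section 3.2.10 allows certain brief courses without PI discussion while 4.6 asks for it, and the antiemetic steroids of 4.2.1 are not among the 4.6 exceptions.

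Finally, the practical effect is hypothetical and the upper bound is simply total enrolment. Section 11.6.2 itself describes a deviation as having no substantive effect on risk or scientific integrity. That supports a minor rating. It is not a reason to leave the text as it is.

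**Conclusion.** The concern holds. As written, the steroid threshold in 4.6 runs opposite to 3.2.10 and names as barred the maintenance doses that the eligibility rule admits. It is an internal inconsistency, almost certainly a drafting slip, and its severity is **minor**.

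The number of patients concerned is unknown. The bounds of 15 overall and 6 prospectively assume the enrolment figures in Section 10.2 and no replacement of patients under Section 4.10. The trial's endpoints, DLT and MTD rules, sample size and success criterion are unaffected. That the intent was to bar doses above 10 mg/day is an inference from 3.2.10 and from the otherwise idle 10 mg/day figure; the documents do not state it.

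**What to change.** In the immunosuppressive bullet of Section 4.6, delete *not* so that the bar applies to systemic corticosteroids at doses exceeding 10 mg/day of prednisone or equivalent. Keep the existing exceptions. The dose threshold then matches 3.2.10, and the conflict with the baseline-medication sentence goes away for doses of 10 mg/day or less.

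If the sponsor wants to leave no room for argument, a short clause can state that 10 mg/day or less is permitted. Antiemetic steroids under 4.2.1 could be added to the list of exceptions at the same time. Neither addition is needed to correct the threshold.

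The cost is one deleted word in a protocol amendment, with no effect on the analysis or the sample size.

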4.7 Duration of Therapy (for both dose- escalation and dose- expansion phase)

Patients may continue with treatment until any of the following occur:

- Disease progression, unless the patient meets criteria for continuing treatment beyond progression. See section 4.7.1 for details.
- Development of an inter-current illness that prevents further administration of treatment
- Unacceptable adverse event(s)
- Patient decides to withdraw from either study treatment or the study as a whole
- The treating investigator determines that the patient should be taken off treatment for any reason (i.e. changes in condition, inability to comply with study treatment or procedures)

4.7.1 Continuation of Investigational Therapy after Progression

In the event of an initial assessment of PD (based on RECIST Version 1.1), a subject may continue to receive the assigned study treatment as long as none of the criteria listed below are met.

1. Confirmed PD: An initial assessment of PD by RECIST 1.1 or Lugano criteria will be confirmed by a repeat evaluation at the next tumor assessment time point, but no sooner than 4 weeks later (see section 6.1.7 & Appendix C, respectively). If any subsequent tumor assessment shows progression per RECIST v1.1 or Lugano criteria in the overall tumor burden (the sum of diameters of target lesions and new lesions), when compared to the initial PD assessment (the sum of diameters of target lesions and new lesions), then PD is confirmed.
2. Meets any of the other investigational product discontinuation criteria (Section 4.6)
3. Clinical symptoms or signs indicating significant PD, for example the benefit-risk ratio of continuing therapy is no longer justified.
4. Decline in ECOG performance status.
5. Threat to vital organs/critical anatomical sites (e.g., spinal cord compression) requiring urgent alternative medical intervention, and continuation of study therapy would prevent institution of such intervention.

4.8 Duration of Follow Up (for both dose- escalation and dose- expansion phase)

After patients come off treatment they will be followed up at 3, 6, 9, 12 months and then every 6 months for 3 years (from the start of the treatment) for survival and progression of disease via either clinic visits or phone calls.

4.9 Removal of Subjects from Study Treatment and/or Study as a Whole (for both dose- escalation and dose- expansion phase)

Patients can be taken off the study treatment and/or study as a whole at any time at their own request, or they may be withdrawn at the discretion of the investigator for safety, behavioral or administrative reasons. The reason(s) for discontinuation must be clearly documented on the appropriate eCRF and may include:

- Patient voluntarily withdraws from treatment (follow-up permitted)
- Patient withdraws consent (no follow-up permitted)
- Patient is unable to comply with protocol requirements
- Patient demonstrates disease progression
- Patient experiences unacceptable toxicity
- Treating physician determines that continuation on the study would not be in the patient's best interest
- Patient becomes pregnant
- Patient develops a second malignancy that requires treatment which would interfere with this study
- Patient becomes lost to follow-up (LTF)

Patients who are permanently discontinued from receiving investigational product will be followed for disease progression and safety, including the collection of any protocol- specified blood specimens, unless consent is withdrawn or the subject is lost to follow-up or administered subsequent therapy. All subjects will be followed for survival and disease progression. Subjects who decline to return to the site for evaluations will be offered follow-up by phone every 3 months as an alternative.

4.10 Patient Replacement

If a patient is enrolled in the study but comes off study before cycle 1 day 1 of

treatment, the patient may be replaced.

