4.2 Treatment Administration

Table 4.1: Dosing of Nivolumab and Veliparib

Drug	Dose	Route	Schedule
Nivolumab (Opdivo)	C1-4: 240mg C5+: 480mg	IV	Cycle 1-4: every 14 days Cycle 5+: every 28 days until progression of disease, intolerable toxicity, or withdrawal of consent
Veliparib	Phase I: Starting dose 300mg (see 4.3 for escalation) Phase Ib: MTD	PO	Twice a day about 12 hours apart starting 7 days before C1D1 (Induction monotherapy) continuing until progression of disease, intolerable toxicity, or withdrawal of consent

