4.3.1 Definition of DLT (Dose limiting toxicity)

Toxicity will be assessed using the National Cancer Institute (NCI) Common Toxicity Criteria for Adverse Events (CTCAE), version 4.03 unless otherwise specified. A DLT is defined as an AE or abnormal laboratory value assessed as at least possibly related to the study medication, occurs ≤ 28 days following the first dose of veliparib and nivolumab and meets any of the criteria listed below. Whenever a patient experiences toxicity that fulfills the criteria for a DLT, treatment with the study drug combination will be interrupted until resolution to ≤ Grade 1 or baseline, and the toxicity will be followed up until resolution. All adverse events specified below will be DLT's except those that are clearly and incontrovertibly due to extraneous causes.

The following events will be considered DLT's:

1. Grade ≥ 3 non-hematologic toxicities that represent at least a 2-grade increase from baseline with the following exceptions:
 - a. Nausea, vomiting, and diarrhea lasting ≤48 hours
 - b. Electrolyte abnormalities resolving within ≤24 hours
 - c. Hypersensitivity reactions
 - d. Alopecia
2. Grade 4 thrombocytopenia (platelets < 25.0 x 10⁹/L)
3. Grade 3 thrombocytopenia with bleeding (platelets <50.0 x 10⁹/L)
4. Grade 4 neutropenia (ANC < 0.5 x 10⁹/L)
5. Grade 3 febrile neutropenia with fever lasting for > 7 days
6. Grade 4 febrile neutropenia of any duration
7. Dosing delay due to toxicity for > 14 consecutive days from the date nivolumab or veliparib is due.

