4.3.2 Dose Escalation 3+3 Rule

Table 4.4: Dose escalation plan based on 3 + 3 design for veliparib and nivolumab

Number of Subjects with DLT in the First Cycle	Escalation Decision Rule
0 out of 3	Enter 3 subjects at the next dose level.
1 out of 3	Add 3 more subjects at current dose level. • If < 2 of 6 subjects (or < 33% of subjects) experience DLT, dose escalation will proceed to the next dose level. • If ≥ 2 of total 6 subjects (or ≥ 33% of subjects) experience DLTs, then dose escalation will be stopped.*
≥ 2 out of 3 or 6	Dose escalation will be stopped.*

*For dose level 1, additional subjects will be enrolled at the previous lower dose level (-1) as needed to establish MTD with 6 patients.

*If dose escalation is stopped at dose level 2, dose level 1 will be established as the MTD if it enrolled 6 patients (<2 of 6 patients had DLT). If dose level 1 enrolled only 3 patients (0 of 3 had DLT's), 3 more patients will be added to dose level 1 to establish the MTD. From there, dose level -1 will be utilized in the case that ≥ 2 patients have DLT.

NOTE: Whichever dose level is declared the MTD must have 6 total patients treated at that level. For example, if 3 patients are treated at level 2 and 0 patients experience DLT, escalation would then proceed to level 3. However, if ≥ 2 patients at level 3 experience DLT, enrollment to level 2 would need to be re-opened to enroll an additional 3 patients at that level (with 0 or 1 DLT observed in 6 total patients) in order to declare level 2 the MTD.

4.3.3 Dose **expansion**:

The initial study design was to accrue a total of up to 50 patients (for 48 evaluable) to the study in two phases: dose escalation and dose expansion. The original design anticipated a total of 6-18 patients with advanced solid tumors or lymphoma in the dose escalation phase. 9 patients were enrolled, including 6 that were treated at the MTD of 400 mg BID.

However, due to funding issues, the study will adopt a modified plan for the expansion cohort, and will perform an early analysis of preliminary efficacy after the next 6 patients are enrolled in the expansion cohort.

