- j. Imaging (either CT scan or MRI and PET if applicable) will be performed at screening, ≤ 28 days prior to registration. The same modality used at baseline should be used throughout for imaging. CT imaging will include chest, abdomen, and pelvis. Neck will be included only if measurable lesions are present. Scans will then take place every 2 cycles (8 weeks) starting with Cycle 3 Day 1 (- 7 days). Tumor measurements will be performed using RECIST 1.1 or Lugano classification. Progressive Disease (PD) must be confirmed by repeat scan within 8 weeks.
- k. Patients will undergo a fresh tissue biopsy prior to study enrollment, unless deemed to be clinically inappropriate per PI. If a fresh biopsy is not feasible, an archival tissue sample should be obtained (a cell block is preferred, however 15 unstained slides will suffice). Tissue should be obtained by any means possible, but patients will not be excluded from the study if tissue is not available. The samples will be obtained for correlative studies – see section 9.0 and separate lab manual for details.
- l. Study labs will be collected for tumor markers pre-dose on Induction Day 1, C1D1, C3D1, and at the End of Treatment visit. See section 9.0 and separate lab manual for more details.
- m. Nivolumab will be administered as follows:
 - Cycles 1-4: given at a fixed dose of 240mg IV over 30 minutes (-5 / +15 minutes) every 2 weeks
 - Starting with Cycle 5 Day 1: 480mg IV over 30 minutes (-10 / +15 minutes) every 4 weeks until disease progression, intolerability, or withdrawal of consent.
 - Vital signs will be monitored prior to, throughout, and after the nivolumab infusion according to Table 4.2.
- n. Veliparib will be taken orally at the assigned dose twice a day until disease progression, intolerability, or withdrawal of consent. It will be initiated as monotherapy during a 7-day induction period. Starting with Cycle 1 Day 1, veliparib will be given twice daily in combination with scheduled nivolumab infusions. Veliparib may be taken with or without food. Patients will be given a drug diary to maintain for compliance. Veliparib dosing may take place independently of nivolumab. On the day of a study visit, lab values should be checked against sections 4.4 and 4.5 for continued dosing.
- o. The end of treatment visit should occur 30 days after the last dose of study treatment (± 7 days) or before starting another line of treatment, whichever comes first.

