6.4 Primary Endpoint

The primary objective is to identify maximum tolerated dose (MTD) for the combination treatment of nivolumab and veliparib.

The MTD will be defined as the highest dose that causes dose-limiting toxicities (DLTs) in <2 of 6 patients and is determined for this study..

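### Section 4.10 lets patients already dosed with veliparib in induction be replaced, so treated non-responders can leave the ORR denominator of the expansion analysis

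*Combined protocol and SAP*

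**What the plan says.** Section 4.10 sets the replacement rule: "If a patient is enrolled in the study but comes off study before cycle 1 day 1 of" treatment, replacement is allowed. It gives no limit by reason, and it does not separate patients who never took study drug from those who did.

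Study drug begins before that day. Table 4.1 in Section 4.2 has veliparib "starting 7 days before C1D1 (Induction monotherapy"), and the footnote on veliparib in Section 5.0 says "It will be initiated as monotherapy during a 7-day induction period".

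Sections 4.3.3 and 10.2 fix the efficacy rule. Six new mutation-positive patients join four already treated at the MTD, giving n = 10. The study succeeds if the exact lower 90% bound on ORR exceeds 10%, which the plan equates with three or more responses. ORR is read at the first imaging, at 8 weeks. Section 10.3 names an ITT population but restricts it to evaluable patients without defining the term. No section says whether a replaced patient stays in or leaves the ORR count.

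The DLT window is worded in two ways. Section 4.3.1 counts an event that "occurs ≤ 28 days following the first dose of veliparib and nivolumab and meets any of the criteria listed below". Table 4.4 in Section 4.3.2 is headed "Number of Subjects with DLT in the First Cycle".

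**The concern.** The replacement cut-off is the first combination dose, not the first dose of study drug, and a week of veliparib lies between the two. The ORR count has ten places: four are filled, and six are left for new patients. If a dosed patient leaves in induction and is replaced, the replacement naturally takes the place and the first patient goes uncounted. An undefined evaluable set does nothing to prevent this.

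A patient who leaves the study in induction has no week-8 scan and so cannot be recorded as a responder. Leaving such patients out can only raise the observed ORR or leave it unchanged. In a rule that turns on a single response out of ten, a shift of one or two in the denominator matters. It also leaves the denominator to be settled after outcomes are known.

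**Working it through.** **Inputs from the documents.** n = 4 + 6 = 10; success if the exact lower 90% bound exceeds 10%, equated with at least 3 responses (Section 10.2); no responses so far at the MTD (Study Summary, sample size); veliparib from 7 days before C1D1 (Table 4.1).

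**Assumed, because the documents give no figure.** The number *k* of patients replaced after induction dosing (0 to 4), or an induction drop-out probability *d* of 5% to 20%.

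**Step 1: reproduce the plan's rule.** The exact (Clopper-Pearson) one-sided 90% lower bound for *x* responses in *n* is the 0.10 quantile of a Beta(*x*, *n* − *x* + 1) distribution.
- 2/10: 5.5%, below 10%
- 3/10: 11.6%, above 10%

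The minimum is 3, as stated. This needs the one-sided reading. The lower limit of a two-sided 90% interval for 3/10 is 8.7%, which would fail.

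**Step 2: keep *k* induction drop-outs as non-responders, with 3 responses observed.**

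| k | x/n | Lower bound | Decision | Responses needed |
|---|---|---|---|---|
| 0 | 3/10 | 11.6% | success | 3 |
| 1 | 3/11 | 10.5% | success | 3 |
| 2 | 3/12 | 9.6% | failure | 4 |
| 3 | 3/13 | 8.8% | failure | 4 |
| 4 | 3/14 | 8.1% | failure | 4 |

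**Step 3: effect of leaving them out on the chance of a false success.** Suppose the true response rate among all dosed patients is 10%, and a fraction *d* leaves in induction without response. The rate among those who reach C1D1 is then 0.10/(1 − *d*). The chance of success is P(X ≥ 3) for X ~ Binomial(10, 0.10/(1 − *d*)).

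| d | Rate among C1D1 starters | P(≥3 of 10) |
|---|---|---|
| 0 | 10.0% | 7.0% |
| 5% | 10.5% | 8.0% |
| 10% | 11.1% | 9.1% |
| 15% | 11.8% | 10.4% |
| 20% | 12.5% | 12.0% |

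This treats all ten patients as still to come. The four already treated had no response, so all three responses must come from the six new patients. With X ~ Binomial(6, *p*), P(X ≥ 3) = 1 − (1 − *p*)^6 − 6*p*(1 − *p*)^5 − 15*p*²(1 − *p*)^4. This is 1.6% at *p* = 10.0%, 1.8% at 10.5% and 2.9% at 12.5%. The relative inflation is similar or slightly larger, but the absolute size is small.

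**Step 4: the DLT window.** If the 28 days in Section 4.3.1 run from the first veliparib dose, induction is inside the window, but the window closes 28 − 7 = 21 days after C1D1, about a week before Cycle 1 ends. If they run from the first day on which both drugs are given, the window matches Table 4.4 and induction is outside it. The text supports either start, and only the second agrees with the table.

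**The case against.** The strongest reply is that being replaceable is not the same as being excluded. Section 4.10 speaks only of replacement, Section 10.3 names an ITT population, and an analyst could keep the replaced patient. Section 4.10 also requires the patient to come off study, which Section 4.9 distinguishes from stopping treatment. The authors may simply have meant patients who never started. All of this is possible, but the text does not settle it. A count fixed at 4 + 6 and an undefined evaluable set make exclusion the easier reading.

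The effect is also limited. One replaced patient changes nothing at 3 responses. A reversal needs at least two, together with exactly 3 responses from the six new patients. Progression within seven days would be mainly clinical and probably rare, since the first on-study scan is at 8 weeks. These limits stand.

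A reader might infer more than the documents support:
- **That the declared MTD is biased.** Section 3.0 reports 9 enrolled, 3 at the lowest dose and 6 at the MTD, with no replaced patient visible. No DLT counts are given, so turning 1 of 6 into 2 of 6 against the definition in Section 6.4 ("The MTD will be defined as the highest dose that causes dose-limiting toxicities (DLTs) in <2 of 6 patients") would be an assumption.
- **That induction toxicity is definitely outside the DLT window.** Step 4 shows this is one of two readings.
- **That induction toxicity is lost.** Adverse events are collected from consent (Section 5.0), so it stays in the safety data. At most it leaves the DLT count.
- **That the delay criterion ("Dosing delay due to toxicity for > 14 consecutive days from the date nivolumab or veliparib is due") cannot be met for the C1D15 nivolumab dose within 28 days.** Section 4.3.1 can be read as timing the adverse event rather than the end of the delay, and the criterion also covers veliparib, which is due twice daily.
- **That only unfavourable outcomes are removed.** Section 4.9 also lists withdrawal of consent, non-compliance and loss to follow-up.

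**Conclusion.** The concern holds for ORR in the six expansion patients. Section 4.10 permits replacement of patients who have taken up to 7 days of veliparib, and nothing in the analysis plan keeps them in the denominator. At 3 responses, two such patients turn success (11.6% at 3/10) into failure (9.6% at 3/12); one does not (10.5% at 3/11). For an assumed induction drop-out of 5% to 20%, and a true rate of 10% among all dosed patients, the chance of a false success over ten patients rises from 7.0% to between 8.0% and 12.0%. Given no response in the first four, it rises from 1.6% to between 1.8% and 2.9%. These figures rest on the one-sided reading of the bound, on drop-outs counting as non-responders, and on drop-out rates that the documents do not supply.

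The DLT point is one of clarity only. Sections 4.3.1 and 4.3.2 do not agree on whether induction events count. The documents do not show that the declared MTD is wrong.

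**What to change.** - **Section 4.10:** limit replacement to patients who never took a dose of veliparib.
- **Section 10.3:** define evaluable. Keep every patient with the required mutation who took at least one dose at the MTD in the ORR denominator, counting the absence of a week-8 response assessment as non-response. State that the exact bound is computed on the number actually in that set, even if it exceeds ten. List any replaced patients with reasons.
- **Sections 4.3.1 and 4.3.2:** reconcile the two descriptions of the DLT window, and report descriptively any induction event that meets DLT criteria. Which window applies is for the sponsor and investigator to settle.

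The cost is a few sentences and no new data collection. ORR may come out slightly lower. If two to four dosed patients leave in induction, 4 responses rather than 3 would be needed for success.
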